8.4 Monitoring of Exploratory Endpoints

We will plan to assess QOL and healthcare resource utilization. Cost data will be obtained at the conclusion of study therapy

8.4.1 QOL: QOL will be assessed after each cycle of remission induction and post-remission therapy, then every 3 months if they remain on maintenance Sorafenib for up to 12 months, and at the conclusion of study treatment by the European Organization for Research and Treatment of Cancer QLQ-C30 questionnaire, a validated QOL measurement for oncology patients (Appendix C) [34]. These questionnaires will be distributed at clinic visits, which will be occurring at least monthly.

8.4.2 Cost: Cost records will be obtained at the conclusion of study treatment from the Financial Services Department.

8.4.3 Healthcare resource utilization: This will be a composite measure. These variables will be recorded (at the end of the study due to time constraints of the data coordinator) to capture the period from the start of treatment to first response assessment (e.g. remission induction). The following variables will be collected: total number of hospital admissions and duration of stays, days in the intensive care unit, number of blood product transfusions received, episodes of febrile neutropenia and days requiring antibiotic use, number of visits to the emergency department, and number of physician or advanced practice provider clinic visits.

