2.3 Exploratory Objectives

- 2.3.1 To assess the feasibility of incorporating QOL, cost and healthcare resource utilization endpoints in to a phase 1/2 clinical trial for newly diagnosed AML.
- 2.3.2 To investigate, within the limits of a phase 1/2 trial, the impact of study treatment and response on quality of life, cost, and healthcare resource utilization for patients with AML undergoing intensive chemotherapy.

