The following studies should be obtained at baseline before initiation of study therapy to establish trial eligibility and allow patient characterization and disease prognostication. Results of tests and/or procedures conducted as per standard of care may be used to determine study eligibility if conducted within an appropriate window prior to screening. Outside testing and previously collected clinical data may be used if within the appropriate time frame.

- 6.1.1 History and physical examination (assessed within 10 days prior to study day 0).
- 6.1.2 Peripheral blood or bone marrow examination with morphologic and flow cytometric assessment, routine cytogenetic analysis, and molecular testing (FLT3/ITD, NPM1, CEBPA, or mutation profiling assay when available); a bone marrow biopsy should be obtained if spicules are absent from the aspirate sample (aspirate and biopsy to be assessed within 2 months prior to study day 0).
- 6.1.2 Complete blood counts with differential blood count and platelet count (assessed within 10 days prior to study day 0).
- 6.1.3 Metabolic panel, including bilirubin, albumin, and creatinine (assessed within 10 days prior to study day 0).
- 6.1.4 MUGA scan or echocardiography, or other appropriate diagnostic modality, to assess left ventricular ejection fraction (LVEF; assessed within 3 months prior to study day 0).
- 6.1.5 For patients with a history of cardiac disease, a baseline ECG is recommended. Further ECG monitoring while taking sorafenib should be done at the discretion of the treating physician and PI, taking into account any concomitant QTc prolongation medications and electrolyte abnormalities.

6.2 **Pre-Treatment**

At the discretion of the treating physician, allopurinol 300 mg PO daily (or equivalent dose adjusted for renal function) may be considered in all patients without known allergies to allopurinol to reduce the risk of tumor lysis. Higher doses of allopurinol are permitted if patients develop tumor lysis syndrome. Patients may receive rasburicase, a recombinant uric acid oxidase, for the prevention and/or treatment of tumor lysis syndrome at the discretion of the treating physician. All patients should be adequately hydrated and receive anti-emetics as necessary.

6.3 **Administration of Sorafenib and Mitoxantrone**

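### No pre-treatment QLQ-C30 is scheduled, so change in quality of life across induction cannot be described; this weakens but does not defeat exploratory objective 2.3.2

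*Combined protocol and SAP*

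**What the plan says.** Section 8.4.1 sets the whole QLQ-C30 schedule. During chemotherapy, "QOL will be assessed after each cycle of remission induction and post-remission therapy"; later, "then every 3 months if they remain on maintenance Sorafenib for up to 12 months, and at the conclusion of study treatment". On logistics it adds: "These questionnaires will be distributed at clinic visits, which will be occurring at least monthly". No visit before treatment is named.

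Section 6.1 opens with "The following studies should be obtained at baseline before initiation of study therapy to establish trial eligibility". It then lists history and examination, blood or marrow studies, blood counts, metabolic panel, ejection fraction and, for patients with a cardiac history, an ECG. No questionnaire is listed.

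Two exploratory objectives use the instrument. Objective 2.3.1 is "To assess the feasibility of incorporating QOL, cost and healthcare resource utilization endpoints" in a trial of this kind. Objective 2.3.2 is "To investigate, within the limits of a phase 1/2 trial, the impact of study treatment and response on quality of life", together with cost and resource use. Section 14.2 plans descriptive summaries only, disclaims power for differences by response, and says the outcomes are recorded to inform a later, larger study.

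**The concern.** An objective about the impact of treatment on quality of life calls for a reference point. This trial has one arm, so there is no concurrent group to supply it, and the patient's own pre-treatment score is the only candidate. The schedule omits it.

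The background (section 1.0, QOL/Resource Utilization Endpoints) argues for measuring quality of life over time and across disease phases, and asks whether being in remission is itself a benefit. Untreated active disease is the one phase that every patient passes through, and it is the phase left unmeasured.

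Three things are at stake: describing what induction does to quality of life, reading the response-group summaries fairly, and giving a later study the spread of change scores and the baseline-to-follow-up correlation that its planning would normally use. The gap cannot be filled afterwards. Most QLQ-C30 items in Appendix C ask about the past week, so a form completed after cycle 1 does not look back to diagnosis.

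**Working it through.** The documents give no sample size, standard deviation, effect size or power for quality of life, so there is no figure of the plan's to reproduce. The check is mainly of text against text.

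**1. Is a baseline scheduled anywhere?** Section 8.4.1 gives three kinds of time point: after a cycle, every 3 months on maintenance, and end of treatment. None precedes treatment. Section 6.1 has no questionnaire. Section 14.2 mentions the scores only as something to be summarised, and Appendix C reproduces the form without a schedule. The overview figure at the front is not shown, so this conclusion covers the readable text only.

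**2. What can and cannot be described under this schedule?**

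- Change from before treatment to after cycle 1: not available for any patient.
- Change on entering remission: not available for patients who respond to cycle 1, who have no score from before response. It is available for patients who respond only after a second course, because their post-cycle-1 score comes first.
- Scores after each cycle by response group: available, without adjustment for baseline self-report.
- Course across later cycles, maintenance and end of treatment: available.
- Completion of scheduled forms, which serves objective 2.3.1: available. Whether patients who later miss forms began worse off by their own report: not available.
- Resource use: section 8.4.3 records it from the start of treatment to first response assessment. That is the same interval over which change in quality of life cannot be described.

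**3. How much could the missing baseline distort a response comparison? (illustration only)** Suppose eventual responders and non-responders differ before treatment by δ standard deviations (SD), the baseline and post-cycle scores correlate at ρ, and response itself has no effect. The expected post-cycle difference is then ρ × δ. Neither input is in the documents; I assume δ from 0.2 to 0.5 and ρ from 0.3 to 0.7.

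- Low end: 0.3 × 0.2 = 0.06 SD.
- High end: 0.7 × 0.5 = 0.35 SD.

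For scale, take the 41 patients of section 14.2, all returning a form. The 95% half-width of the unadjusted difference is 1.96 × √(1/n₁ + 1/n₂) SD.

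- 25 responders and 16 others (null rate: 0.60 × 41 = 24.6): 0.63 SD.
- 31 and 10 (the success threshold in section 14.2): 0.71 SD.
- 33 and 8 (target rate: 0.80 × 41 = 32.8): 0.77 SD.

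On these assumptions the distortion is smaller than the sampling uncertainty throughout. The clearer loss is therefore the missing description of change across induction. I count no gain in precision from adjustment, since section 14.2 plans no inference on these scores.

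**The case against.** The strongest reply is that the plan promises little. Objective 2.3.2 is exploratory and carries its own qualifier, section 14.2 is descriptive and disclaims power, and nothing in the dose, stopping or phase 2 rules uses the scores. All of this stands and sets the severity. It does not explain the omission, because a descriptive change score also needs a starting value.

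A reader might infer that 2.3.2 cannot be met at all. The documents do not support that: post-cycle scores by response and the later within-patient course remain available.

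A reader might also infer that response groups cannot be compared allowing for illness at diagnosis. That is too strong. Section 3.1.4 requires a treatment-related mortality score for every patient, and Appendix A builds it from performance status, age, albumin, counts and other severity measures. Section 6.1 adds cytogenetic and molecular characterisation. What is missing is narrower: baseline self-reported quality of life.

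The silence of section 6.1 is weak evidence on its own. That list serves eligibility and prognosis, and the questionnaire is equally absent from the monitoring and follow-up lists in sections 6.5 to 6.7 and 6.13, where it is planned. The point therefore rests on section 8.4.1.

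Finally, a baseline would not isolate a treatment effect. In a single arm, change from baseline still mixes treatment, disease control and recovery from acute illness. That stands and limits what the fix can deliver.

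**Conclusion.** The point holds as a minor one. On the readable text, every patient who follows the schedule lacks a pre-treatment QLQ-C30. Change across induction cannot be described, and response-group summaries cannot take baseline self-report into account. Objective 2.3.2 and the aim of informing a larger study are weakened but remain partly achievable; objective 2.3.1 is largely unaffected. The primary endpoint and all trial decisions are untouched.

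The conclusion about the schedule needs no numerical assumption, only that the figure not shown adds no baseline form. The 0.06 to 0.35 SD range rests wholly on assumed inputs and should not be cited as an estimate for this trial.

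**What to change.** Add the QLQ-C30 to sections 6.1 and 8.4.1, to be completed between consent and the first study treatment (Day 0). In section 14.2, add a descriptive summary of change from baseline, overall and by response group, and report the proportion of patients with a baseline form. State beside it that change in a single arm does not separate treatment from disease and recovery.

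For patients already treated without a baseline, limit objective 2.3.2 to description after induction and do not attempt to reconstruct a score.

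The cost is one extra 30-item form per patient. The form is already in Appendix C, and section 6.1 already calls for a history and examination within 10 days before Day 0. Some acutely ill patients will miss it, and they are unlikely to be typical, which is why baseline completion should be reported.

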8.5 Duration of Follow-up

Patients will be followed after completion of study treatment to determine EFS and RFS (for patients achieving CR) as well as overall survival (for all patients) for a maximum of 5 years. Follow-up may include periodic (e.g. every 3 months) review of medical records, and, if absolutely necessary, direct contact of the study participant.

9.0 RECORDS

Research data will be recorded in a study-specific, password protected database using a unique study ID for each patient to assure patient confidentiality. Data from source documents will be transcribed into this database. Source documents are documents where patient data are recorded and documented for the first time. They include, but are not limited to, hospital records, clinical and office charts, laboratory notes, memoranda, quality of life assessments, pharmacy dispensing records, recorded data from automated instruments, copies of transcriptions that are certified after verification as being accurate and complete, X-rays, patient files, and records kept at the pharmacy, laboratories, and medico-technical departments involved in the clinical trial.

Any publication or presentation will refer to patients by this number and not by name. The licensed medical records department, affiliated with the institution where the patient receives medical care, maintains all original inpatient and outpatient chart documents. Patient research files will be maintained under control of the Principal Investigator and/or study team and kept in a locked office or file room within a secure building. Access to the study database will be restricted by electronic password protection and restricted access to computers (i.e., locked offices).

10.0 PROTOCOL ENROLLMENT AND SPECIAL CONSIDERATIONS

All eligible patients will be included in this study without regard to gender or ethnicity. The incidence of AML is slightly higher in men, so it is expected that the distribution of these patients will reflect a slight male predominance of the disease as well as the general demographic distribution of AML patients seen at our institution. Up to 84 patients with newly diagnosed AML/high-risk MDS/MPN will be enrolled in this study. This is an approximate number as it depends on the number of patients enrolled below the MTD in phase 1.

Projected Target Accrual ETHNIC AND GENDER DISTRIBUTION CHART

TARGETED / PLANNED ENROLLMENT: Number of Subjects: 84			
Ethnic Category	Sex / Gender		
	Females	Males	Total
Hispanic or Latino	1	2	3
Not Hispanic or Latino	33	48	81
Ethnic Category Total of All Subjects*	34	50	84
Racial Categories			
American Indian / Alaska Native	0	0	0
Asian	1	1	2
Native Hawaiian or Other Pacific Islander	0	0	0
Black or African American	1	1	2
White	32	48	80
Racial Categories: Total of All Subjects*	34	50	84

*The “Ethnic Category Total of All Subjects” must be equal to the “Racial Categories Total of All Subjects.”

11.0 GUIDELINES FOR SERIOUS ADVERSE EVENT REPORTING

11.1 Expedited Reporting Requirements

In accordance with FHCRC/UW Cancer Consortium IRB policy, all adverse events (AEs; whether occurring on-site or off-site), which in the opinion of the principal investigator (PI) are (1) unexpected, and (2) related or possibly related to the research, and (3) serious or suggests that the research places research participants or others at a greater risk of physical or psychological harm than was previously known or recognized, will be submitted to the IRB within ten (10) calendar days of learning of the problem. Both the “Expedited Reporting Form for Unanticipated Problems or Noncompliance” and the “Adverse Event Reporting Form”, or equivalent forms, will be completed for this reporting.

11.2 Definitions

11.2.1 Adverse Event (AE): Any harm or untoward medical occurrence in a research participant administered a medical product, medical treatment or procedure even if it does not necessarily have a causal relationship with the product, treatment, or procedure. An adverse event can be any unfavorable and unintended sign (including an abnormal laboratory finding, for example), symptom, or disease temporally associated with the use of a medical product, medical treatment, or procedure whether or not considered to be related. Mechanisms of obtaining information on AE include monthly transcripts, assessment forms obtained after each clinic visit, and hospital progress and discharge notes.

11.2.2 Related or Possibly Related AE: An AE is “related or possibly related to the research procedures” if in the opinion of the principal investigator, it was more likely than not caused by the research procedures. AEs that are solely caused by an underlying disease, disorder or condition of the subject or by other circumstances unrelated to either the research or any underlying disease, disorder or condition of the subject are not “related or possibly related”. If there is any question whether or not an AE is related or possibly related, the AE should be reported.

11.2.3 Serious AE (SAE): An adverse event that results in any of the following outcomes:

- Death
- Life-threatening adverse event (real risk of dying)
- Prolongation of hospitalization*
- Persistent or significant disability/incapacity/or change in psychosocial status
- Congenital anomaly
- Requirement of intervention to prevent permanent impairment of damage

*Hospitalization itself will not be considered a serious adverse event if required for complications of AML or comorbid conditions. Hospitalization will be considered a SAE if it fulfills the criteria for a serious and unexpected adverse event as otherwise described.

11.2.4 Unexpected AE: An AE is “unexpected” when its nature (specificity), severity, or frequency are not consistent with (a) the known or foreseeable risk of adverse events associated with the research procedures described in the protocol-related documents, such as the IRB-approved research protocol, informed consent document, and other relevant sources of information such as product labeling and package inserts.

11.2.5 Management of Adverse Events. Please see Appendix D for prevention/management strategies for adverse events common with sorafenib.

Grade ≥ 3 adverse events other than hematologic toxicities will be recorded, graded, and reported as appropriate. AEs will be collected from the time of consent until 60 days after day 1 of each cycle or until the patient receives an alternative anti-cancer therapy, whichever date comes first. AEs that do not meet the requirement for expedited reporting will be reported to the IRB as part of the annual renewal of the protocol.

Myelosuppression and associated complications are expected events during leukemia therapy; therefore, myelosuppression and associated simple complications such as fever,

infections, bleeding, and related hospitalizations will not be reported as individual AE but will be summarized in the annual report to the IRB.

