- 6.3.1 For induction: patients will receive sorafenib and mitoxantrone at 1 of 6 total dose levels as allocated (see section Dose Escalation Scheme page 2 or 15.1.2). Mitoxantrone will be given IV daily over 60 minutes Days 1-3 and sorafenib orally Days 10-19 for all levels. Allowances of +/- 2 days for this window will be allowed for logistical purposes. Levels are as follows: Level 1, mitoxantrone 10 mg/m² with sorafenib 200 mg PO twice daily; Level 2, mitoxantrone 12 mg/m² with sorafenib 200 mg PO twice daily; Level 3, mitoxantrone 15 mg/m² with

sorafenib 200 mg PO twice daily; Level 4, mitoxantrone 18 mg/m² with sorafenib 200 mg PO twice daily; Level 5, mitoxantrone 18 mg/m² with sorafenib 400 mg PO in the morning and 200 mg in the evening; Level 6, mitoxantrone 18 mg/m² with sorafenib 400 mg PO twice daily. Level -1, dosed at mitoxantrone 10 mg/m² and sorafenib 200 mg PO once daily will also be available for dose de-escalation due to toxicities, as described in Section 6.8. For baseline organ dysfunction within the allowable limits of the eligibility criteria, dose reduction of individual medications specific to the organ impairment (e.g. liver, kidney) are allowed but not required, as described in section 6.10, and should be done in conjunction with the Oncology Pharmacist and PI.

- 6.3.2 The dose of mitoxantrone is calculated using the patient's actual weight.
- 6.3.3 For post-remission therapy: sorafenib will be given per dose level as above, starting on day 8 until day 27 or 3 days prior to next cycle of treatment, whichever occurs first. Allowances of +/- 3 days for this window will be allowed for logistical purposes (i.e. timing of clinic visit for count evaluation).
- 6.3.4 For maintenance: sorafenib will be given daily for up to 12 months following post-remission at the final dose the patient received during induction, with subsequent dose adjustment based on blood counts and extra-medullary toxicities.
- 6.3.5 All treatment is given as intent-to-treat; missed doses will not be made up.

6.4 **Administration of G-CSF, Cladribine, and Cytarabine**

- 6.4.1 The doses of the elements of G-CLAM chemotherapy will be as follows: G-CSF 5 µcg/kg rounded to 300 or 480 µcg daily subcutaneously daily on Days 0-5, Cladribine 5 mg/m² IV daily over 2 hours on Days 1-5, and Cytarabine 2 g/m² IV daily over 2 hours on Days 1-5.
- 6.4.2 The doses of G-CSF, cladribine, and cytarabine are calculated using the patient's actual weight.

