MRDneg CR. The probability of declaring a therapy of interest when it is not is 10% (type-1 error), and not of interest when it is, is 20% (power 80%). Under the null hypothesis (true MRDneg CR rate 60%) the probability of termination before enrolling 41 patients is 51% and the average sample size is 29 patients. Note that patients treated at the recommended sorafenib and mitoxantrone doses during the Phase 1 part of the study would count toward the first 19 patients. Patients will be considered not evaluable if they received less than 75% of the assigned doses of each chemotherapeutic agent during Cycle 1, and they will be replaced. If a patient does not receive at least 75% of their assigned dose of sorafenib but discontinues the drug due to toxicity, they will be considered evaluable as we want to capture this essential toxicity data (and its potential downstream effect on efficacy) and not be replaced.

QOL scores, resource utilization, and cost variables will be recorded and summarized using descriptive methods including boxplots, histograms, and statistical summary measures (medians, means, standard deviation, N, and proportions). This study will not be powered to detect statistically significant differences between these endpoints for those with different responses; rather we will record these outcomes to inform a subsequent larger study, should follow up investigations be warranted.

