APPENDIX D: MANAGEMENT OF TOXICITIES SPECIFIC TO SORAFENIB

I. Prevention/management strategies for diarrhea and fatigue

Diarrhea and fatigue are common side effects of sorafenib. The same dose-modification algorithm used for skin toxicities can be used to address these toxicities. However, the preventive/management strategies for diarrhea and fatigue should be consistent with local standards (e.g., anti-diarrheals and optimized hydration status for diarrhea).

II. Hand-foot-skin reaction: Suggested sorafenib dermatologic toxicity modification

Recommended dose modification for hand foot skin reaction (HFSR)		
Toxicity Grade		Suggested dose modification
Grade 1	Any occurrence	Maintain dose level and consider topical therapy for symptomatic relief
Grade 2	1 st occurrence	Maintain dose level and consider topical therapy for symptomatic relief If no improvement within 7 days, see below
	No improvement within 7 days or 2 nd occurrence	Interrupt until resolved to Grade 0-1 When resuming treatment, decrease dose by one dose level
	3 rd occurrence	Interrupt until resolved to Grade 0-1 When resuming treatment, decrease dose by two dose levels
	4 th occurrence	Discontinue treatment permanently
Grade 3	1 st occurrence	Interrupt until resolved to Grade 0-1 When resuming treatment, decrease dose by one dose level
	2 nd occurrence	Interrupt until resolved to Grade 0-1 When resuming treatment, decrease dose by two dose levels
	3 rd occurrence	Discontinue treatment permanently

At first occurrence of HFSR, independent of grade, prompt institution of supportive measures such as topical emollients, low potency steroids, or urea-containing creams should be administered.

Recommended prevention/management strategies for skin toxicities consistent with HFSR are summarized below.

Recommended Prevention/Management Strategies for Skin Toxicities Consistent with Hand-Foot-Skin-Reaction	
Toxicity Grade	Practical Prevention / Management Strategies for HFSR
Grade 0 (Preventive strategies)	
 • Maintain frequent contact with trial physician to ensure early diagnosis of HFSR. • Practical prevention strategies 
 ◦ Pedicure^a for subjects with pre-existing hyperkeratosis. ◦ Subjects should avoid hot water, and clothing or activities that can cause friction on the skin. ◦ Moisturizing cream should be applied sparingly. • Padded gloves and open shoes with padded soles should be worn to relieve pressure points.

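### Grade 2 events and maintenance cytopenias can change sorafenib dosing, but the plan does not collect them as individual adverse events, so the safety analyses cannot show this intolerance

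*Combined protocol and SAP*

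**What the plan says.** **What is recorded.** Section 11.2.5 covers events of Grade 3 or higher; at that level, "adverse events other than hematologic toxicities will be recorded, graded, and reported as appropriate". Myelosuppression and its simple complications are treated as expected in leukemia therapy: "infections, bleeding, and related hospitalizations will not be reported as individual AE but will be summarized in the annual report to the IRB".

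**What changes sorafenib dosing.** Section 11.2.5 itself points to Appendix D, which acts below Grade 3.
- Hand-foot skin reaction, Grade 2. For "No improvement within 7 days or 2 nd occurrence", the suggested action is "Interrupt until resolved to Grade 0-1 When resuming treatment, decrease dose by one dose level". A third occurrence leads to a two-level cut, and a fourth to "Discontinue treatment permanently".
- Diarrhea and fatigue. Part I of the appendix says that the hand-foot algorithm can be applied.
- Hypertension. Symptomatic or persistent Grade 2 hypertension leads to a hold and a restart one level lower.
- Maintenance. Section 6.3.4 allows up to 12 months of daily sorafenib, "with subsequent dose adjustment based on blood counts and extra-medullary toxicities". The overview in 6.0 says the same and names cytopenias.

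**What the safety data are for.** Objective 2.2.2 is the toxicity profile and adverse event rate of sorafenib with G-CLAM. Section 14.1.1 reviews Grade 3 or higher events for late and cumulative toxicity before phase 2 begins. Section 14.2 says of patients who receive under 75% of their sorafenib and discontinue it for toxicity that "they will be considered evaluable as we want to capture this essential toxicity data".

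**The concern.** The recording threshold is higher than the threshold at which the protocol acts. A patient could have repeated Grade 2 hand-foot reactions, step down two dose levels and finally stop sorafenib without any of those reactions entering the adverse event data. A patient on maintenance could have the dose changed for low counts with no individual record of the cytopenia.

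Such events bear on whether patients can stay on sorafenib, which here means repeated post-remission courses and up to a year of maintenance. If they are not collected, the report under objective 2.2.2 will describe severe toxicity but not the lower-grade toxicity that altered treatment. The review meant to find cumulative problems before phase 2 will have the same gap.

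**Working it through.** No sample size, power or rate enters this point, so there is nothing to calculate. The check sets each trigger for a sorafenib change against every place where the documents capture toxicity.

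| Trigger | Effect on sorafenib | Individual AE record under 11.2.5 | Other trace |
|---|---|---|---|
| Grade 2 hand-foot reaction, unimproved at 7 days or second occurrence | Interrupt, resume one level lower | None | Diary (Appendix E) shows doses taken, not cause or grade |
| Same, third occurrence | Interrupt, resume two levels lower | None | As above |
| Same, fourth occurrence | Permanent stop | None | Reason documented under 6.14 if protocol treatment ends; no grade required |
| Grade 2 diarrhea or fatigue | Same algorithm can be used | None | As above, by action |
| Symptomatic or persistent Grade 2 hypertension | Hold, restart one level lower | None | Anti-hypertensive drugs noted in the patient's records |
| Cytopenia during maintenance | Dose adjusted | None | Counts at least monthly (6.13.1); annual IRB summary |
| Grade 3 or higher non-hematologic event | Interrupt, reduce or stop, by event | Yes, within the collection window | Not needed |
| Prolonged cytopenia beyond 49 days without disease (8.3.3) | Counts as a DLT | Captured as a DLT; Cycle 1 DLTs guide escalation | Not needed |

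The gap is in the first six rows. Tracing it to the three uses of the data:

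1. **Objective 2.2.2.** A profile built from the recorded events contains none of the first six rows. It can be correct for Grade 3 or higher non-hematologic events and still give no account of lower-grade events that caused holds or reductions.
2. **Section 14.1.1.** The review covers Grade 3 or higher events only. A run of Grade 2 events that forces stepwise reductions is cumulative toxicity, but it falls outside the review.
3. **Section 14.2.** A patient below 75% of sorafenib stays evaluable if the drug was discontinued for toxicity. If that toxicity was Grade 2, it helps decide whether the patient remains in the primary analysis, yet the event is not in the adverse event data.

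Section 6.14 does not close the gap. It requires reasons for discontinuing treatment but is silent on holds and reductions, and it does not clearly cover stopping sorafenib alone while other protocol treatment continues.

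A related point bears on the fix. The window in 11.2.5 is stated by cycle: "AEs will be collected from the time of consent until 60 days after day 1 of each cycle". The documents define no maintenance cycle, so whether the window spans maintenance depends on how a cycle is counted there.

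**The case against.** The Grade 3 threshold is a deliberate and consistent choice: 11.2.5 and 14.1.1 match, and objective 2.2.2 does not promise all grades. Non-hematologic DLTs in 8.3 start at Grade 3, so recording Grade 2 events would not change dose escalation. Those points stand.

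Other capture also exists. Reasons for discontinuing treatment must be documented without a grade limit, and 6.14.7 lists toxicity as a reason. The diary, returned bottles and dispensing records (9.0) would reveal missed doses. Cytopenias could be derived from laboratory values. Section 11.1 covers unexpected, related events of any grade that suggest greater risk. These leave traces, but none requires the event and grade behind a sub-Grade 3 hold or reduction, or ties a maintenance dose change to its cytopenia.

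The hand-foot modifications are labelled suggested or recommended, and their use for diarrhea and fatigue is optional. This makes the number of such changes uncertain. The hypertension table, however, is introduced as the schedule to follow.

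A reader might infer more than the documents support:
- That the toxicities limiting sorafenib are missing altogether. They are not: Grade 3 or higher non-hematologic toxicity is recorded.
- That half the toxicity is lost, because three of the six hand-foot rows that interrupt, reduce or stop sorafenib are Grade 2. Table rows are not event frequencies.
- That a short Grade 2 hold would commonly take a patient below 75% of the 10-day induction block. The documents give no hold length, and a first Grade 2 hand-foot reaction keeps the dose unless it has not improved within 7 days.
- That most patients could fail to stay on a dose that looks well tolerated. No rate supports this.

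**Conclusion.** The point holds in a limited form. For Grade 2 events that lead to a sorafenib interruption or reduction, and for cytopenias that change the maintenance dose, the plan requires no individual adverse event record. That statement concerns individual records only: reasons for discontinuing treatment are documented, and myelosuppression is summarized annually for the IRB. Objective 2.2.2 and the 14.1.1 review therefore cannot show sub-Grade 3 sorafenib intolerance, which sits poorly with the intent stated in 14.2.

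The size cannot be given as a number, because the documents contain no frequency for these events. Neither the MTD rule nor the definition of MRDneg CR uses the missing data. The link from maintenance cytopenias to the phase 2 dose is weak, since maintenance follows up to four post-remission courses and phase 2 may start before such data exist.

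The conclusion assumes that 11.2.5 is the operative collection rule and that no case report form outside these documents already asks for the reason and grade of each sorafenib change. If one does, the gap is in the written plan rather than in the data. This is an inexpensive improvement to data collection and should be made.

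**What to change.** - **11.2.5:** add that adverse events of any grade, including cytopenias, that lead to interruption, reduction or discontinuation of sorafenib are recorded with grade, date and action taken. State that this applies for as long as the patient receives sorafenib, maintenance included.
- **14.1.1:** include those of these events available at the time in the review before phase 2.
- **Objective 2.2.2:** report the proportion of patients with a sorafenib hold, reduction or stop for toxicity, alongside the Grade 3 or higher rates.

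The cost is a few extra adverse event lines per patient, for events the site is already acting on. Visits, tests, doses and clinical rules stay as they are.
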